9.5.4. Safety analysis methodology

Safety analyses will be based on the Safety Set.

The safety and tolerability profile will be assessed versus baseline conditions and differences between treatment groups. Descriptive statistics will be produced, where applicable.

Bone Mineral Density loss will be compared between the OBE2109 treatment groups and placebo in terms of percent change from baseline. In addition, a confidence interval for the percent change from baseline within each group will be produced.

Effect of the add-back therapy versus placebo will be assessed by comparing on one hand the OBE2109 200 mg + E2 1 mg/NETA 0.5 mg versus the OBE2109 200 mg group alone, and on the other hand, the OBE2109 100 mg + E2 1 mg/NETA 0.5 °mg versus the OBE2109 100 mg group alone on bone mineral density loss.

An analysis of covariance model including the baseline BMD and stratification factor race as a covariate will be used.

Extent of exposure and compliance will be evaluated.

9.5.5. Missing Data

In order to take into account all randomized subjects in the analysis, the assessment of the primary endpoint for subjects who do not have menstrual bleeding data up to Week 24 (and who did not discontinue prematurely due to lack of efficacy or adverse events, or undergo operative or radiological interventions for uterine fibroids) will be based on the results from the last 28 days prior to the last diary completion. Subjects who have less than 28 days of data will be treated as non-responders. The secondary endpoint of amenorrhea will be assessed in a similar way.

Missing values for continuous efficacy endpoints analyzed via likelihood methods (e.g. repeated measures mixed models) will not be directly imputed as they are handled within the analysis itself, under the assumption that the model specification is correct and that the data is missing at random.

Sensitivity analyses will be conducted to check the robustness of the analysis results under alternative assumptions with regards to missing data. Further details on the handling of missing values and planned sensitivity analyses will be defined in the SAP.

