3. ENDPOINTS

3.1. EFFICACY ENDPOINTS

3.1.1. Primary

Reduced menstrual blood loss at 24 weeks of treatment (last 28 days prior to Week 24 visit) defined as menstrual blood loss \leq 80 mL and \geq 50% reduction from baseline.

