6.5.2. Prohibited Medicines

Medication listed in the exclusion criteria (see Section 5.2.2) will be prohibited up to Week 52.

To consider a subject who is currently taking any prohibited therapies for potential inclusion in this study, the Investigator must ensure that the subject has sufficient washout time prior to screening (see Section 5.2.2).

Strong CYP3A inhibitors or inducers are prohibited up to 4 weeks after end of treatment in view of the add-back treatment (APPENDIX H).

OATP1B1/1B3 inhibitors (e.g. clarithromycin, erythromycin, gemfibrozil, telithromycin) are prohibited during the treatment period only (APPENDIX I).

When a prohibited medication or treatment is necessary for the subject's well-being, the Sponsor must be notified and possible alternatives are to be discussed before administration of the prohibited medication or treatment whenever possible.

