6.6.2.1. Discontinuation criteria

During the course of the study, the subject may be discontinued for the following reasons to be reported in the eCRF Study Termination Form:

-	Lack of Efficacy:	Investigator's judgment only. If subject's opinion only, check subject's Request. Explain in the specify field.
-	Adverse Event:	Includes clinically significant new or worsening existing condition as judged by the Investigator. Document also in the AE form.
-	Subject's Request:	Consent withdrawal, subject moved, schedule conflicts, etc. Specify the reason in the comment section of the eCRF Exit Form.
-	Protocol Violation:	Major protocol violation which may affect the subject's safety. Specify the protocol violation in the comment section of the eCRF Exit Form.
-	Lost to Follow-up:	Document with two phone calls and a certified letter requesting return receipt without response. Document in the comment section of the eCRF Exit Form.
-	Pregnancy:	Subjects that have been exposed to study treatment and who become pregnant during the treatment period will be immediately withdrawn from treatment. Pregnancies that have been exposed to study treatment and/or started before the Week 64 visit or in case of early withdrawal up to 4 weeks after treatment discontinuation will be followed up for pregnancy and neonatal outcomes at birth. Any pregnancy must be reported with the Pregnancy Surveillance Form (see section 8.6).
-	Other:	Specify in the Comments section in the eCRF Exit Form. This reason should only be used if the reason for discontinuation is not better accounted for by another category.

Subjects presenting with alanine aminotransferase (ALT), aspartate aminotransferase (AST), gammaglutamyl transpeptidase (GGT) or total bilirubin ≥ 2 times the upper limit of normal at Day 1 will have to discontinue study treatment once these results are received by the study site. Subjects presenting with a Z-score \leq -2 assessed on the DXA at Day 1 will have to discontinue study treatment.

Subjects presenting with a clinically significant finding in the biopsy sample collected at screening and who have completed Day 1, will have to discontinue study treatment.

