9.5.2. Primary Efficacy Analysis

The primary analysis set for the efficacy analyses will be the Full Analysis Set.

The primary analyses of reduced menstrual blood loss at 24 weeks of treatment (last 28 days prior to week 24 visit) will be analysed as a categorical variable (yes / no response) and will be conducted as follows:

Cochran-Mantel-Haenszel (CMH) tests with adjustment for the stratification factor race will be used to test the null hypothesis of no treatment effect for each OBE2109 group vs. placebo with regards to the

proportion of subjects with a reduced menstrual blood loss at 24 weeks. The odds ratios will be estimated from the CMH test together with the associated 95% CI and corresponding p-values. The proportion per treatment arm will be displayed together with exact Clopper-Pearson 95% CIs. The differences in percentages with corresponding 95% Newcombe-Wilson confidence intervals will also be presented. The homogeneity of the odds ratios will be explored using the Breslow-Day test.

In addition to the CMH tests and to further explore a possible interaction between race and treatment, a logistic regression model with terms for treatment, stratification factor race and the interaction between treatment and race will be fitted to the binary response data. Contrast and estimate statements will provide separated tests for each OBE2109 group vs. placebo for each strata. In case of too many empty cells or non-convergence of the model, separated Fisher's exact tests will be used for each comparison versus placebo, within strata. Subjects who discontinue prematurely due to lack of efficacy or adverse events, or who undergo operative or radiological interventions for uterine fibroids, will be considered as non-responders.

In order to account for multiplicity given four different OBE2109 treatment groups, each primary endpoint comparison versus placebo will be conducted at the 0.0125 level of significance, i.e. 0.05 divided by 4.

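### The non-responder rule for the primary endpoint omits women who stop because they themselves see no benefit, women who become pregnant, and users of prohibited bleeding-reducing drugs

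*Protocol*

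**What the plan says.** Section 3.1.1 sets the primary endpoint as response in the 28 days before the Week 24 visit: blood loss of at most 80 mL and a fall of at least 50% from baseline. Section 6.3 bases all bleeding endpoints on alkaline hematin data.

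Section 9.5.2 names the withdrawals and events that count as non-response: "Subjects who discontinue prematurely due to lack of efficacy or adverse events, or who undergo operative or radiological interventions for uterine fibroids". Section 9.5.5 adds: "Subjects who have less than 28 days of data will be treated as non-responders". For any other woman without data to Week 24, the assessment "will be based on the results from the last 28 days prior to the last diary completion". The diary therefore only dates the window; the volume comes from the hematin assay. Section 9.5.5 says amenorrhea is handled similarly.

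Section 6.6.2.1 lists the withdrawal codes. Under Lack of Efficacy it instructs: "Investigator's judgment only. If subject's opinion only, check subject's Request". Pregnancy is a separate code: "Subjects that have been exposed to study treatment and who become pregnant during the treatment period will be immediately withdrawn from treatment".

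On drugs, section 6.5.2 states: "Medication listed in the exclusion criteria (see Section 5.2.2) will be prohibited up to Week 52". When one is nevertheless needed, the section asks for the sponsor to be notified and alternatives discussed. It does not mention response status.

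**The concern.** The rule in 9.5.2 and 9.5.5 is meant to keep treatment failures, and outcomes produced by something other than study drug, from counting as response. As written it stops short of that in three places.

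- A woman who leaves because she feels no benefit is a treatment failure in her own judgment, but the coding instruction places her outside the rule. The investigator, whose judgment alone opens the Lack of Efficacy code, does not see hematin results from Study Day 1 onward (sections 4, 7.8 and 9.6).
- Pregnancy removes menses whatever the treatment. A window that falls after conception can meet the response definition and, over at least 35 days, the amenorrhea definition in 6.3.1.2.
- A prohibited drug that reduces bleeding can produce the response. A procedure is counted as failure; such a drug is not.

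What is at stake is the meaning of the Week 24 response rate in the primary (Full Analysis Set) comparison. Some responses would come from an earlier window or from a cause other than the assigned treatment.

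**Working it through.** **Codes against the rule.** Section 6.6.2.1 has seven codes. Two (Lack of Efficacy, Adverse Event) lead to non-response. Five (Subject's Request, Protocol Violation, Lost to Follow-up, Pregnancy, Other) lead to the last 28-day window, provided there are 28 days of data and no procedure.

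**The three groups.**

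| Group | Where the protocol puts her | How she is scored |
|---|---|---|
| Sees no benefit, investigator does not judge lack of efficacy | Subject's Request (6.6.2.1) | Last 28 days before last diary entry |
| Pregnant, treatment withdrawn | Pregnancy (6.6.2.1, 8.6) | Same, if data stop before Week 24 |
| Used a prohibited bleeding-reducing drug | Protocol deviation (5.2.2 item 16, 6.5.2) | Her own window, unadjusted |

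The third group may have a complete Week 24 window. For those women the problem is a confounded window, not an early one.

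**The protocol's own sample size.** Inputs from 9.2: 30% v 70%, alpha 0.0125 per comparison (two-sided, 9.5), at least 90% power for all four. Per-comparison power is 0.9^(1/4) = 0.974.

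n = [z(α/2)·√(2·p̄·q̄) + z(power)·√(p1q1 + p2q2)]² / d²

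= [2.498 × 0.7071 + 1.943 × 0.6481]² / 0.16, about 57.2, so 58 per arm; 63 with continuity correction. Exact Fisher power at 64 is 0.975 per comparison, and 0.975⁴ is about 0.904. The stated 64 is reproduced.

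**Size of a stricter rule.** The protocol gives no dropout rate and no split by reason, so the share m is an assumption. Let a share m of each arm be scored at the arm's planned rate and then be recoded as non-responders. The rate becomes p(1 − m). Power at n = 100 per arm is

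Φ{ [d·√n − 2.498·√(2·p̄·q̄)] / √(p1q1 + p2q2) }.

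Example, m = 10%: 0.30 × 0.9 = 0.27 and 0.70 × 0.9 = 0.63, so d = 0.36 and p̄ = 0.45. Then (3.6 − 2.498 × 0.7036) / 0.6559 = 2.81, power 0.9975.

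| m placebo / active | Rates | Difference | Power |
|---|---|---|---|
| 0 / 0 | 30% v 70% | 40 points | 0.9997 |
| 5% / 5% | 28.5% v 66.5% | 38 | 0.999 |
| 10% / 10% | 27% v 63% | 36 | 0.9975 |
| 15% / 15% | 25.5% v 59.5% | 34 | 0.994 |
| 20% / 20% | 24% v 56% | 32 | 0.988 |
| 5% / 20% | 28.5% v 56% | 27.5 | 0.933 |
| 20% / 5% | 24% v 66.5% | 42.5 | above 0.999 |

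These rows recode every woman in the share. For a given share under carry-forward, recoding only some of those withdrawals changes less.

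**Size of a carry-forward excess.** If 10% per arm were carried at 85% on active (assumed) and 30% on placebo, active becomes 0.9 × 0.70 + 0.1 × 0.85 = 71.5%, a difference of 41.5 points instead of 40.

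**The case against.** The strongest reply is that carried-forward women are still judged on measured blood loss. A woman who leaves while bleeding heavily fails on her own last window. Only one who met both criteria but felt no benefit is counted a responder. This stands, and it narrows the first gap.

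Several stronger readings are tempting, but the protocol does not support them:

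- *Most dropouts are carried forward.* This is true of reason codes (five of seven). No figures allow a count of women.
- *Active-arm leavers are usually carried as responders, so the bias favours drug.* Section 1.5.1 reports estradiol reduction within a week in healthy volunteers, not blood loss in leavers. In section 1.5.2, the 100 mg dose suppressed menstruation in 8 of 12 women with fibroids. The direction is not shown.
- *A pregnant woman is always scored a responder and amenorrheic.* That holds only if the relevant interval was free enough of bleeding. Contraception is required and pregnancy is tested at visits, so numbers may be small.
- *The fall from 40 to 36 points measures the bias.* It is the effect of setting a tenth of each arm to failure. With more dropout on placebo the same rule raises the difference, to 42.5 points in the table. Blanket non-responder imputation as primary is partly a choice of estimand.
- *The same women should be recoded as never reaching the time-to-event endpoints.* Section 9.5.3 dates the event when it occurs, so this would erase observed events.

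The Per Protocol analysis (7.7, 9.4, 9.6) may exclude drug users, and 9.5.5 promises sensitivity analyses with details in the SAP. Both help, but neither alters the primary rule, which the protocol itself fixes for the Full Analysis Set.

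**Conclusion.** The concern holds in a limited form. The coding instruction in 6.6.2.1 works against the non-responder rule in 9.5.2 and 9.5.5, and the rule does not cover pregnancy or prohibited bleeding-reducing drugs. Followed as written, it can score some of these women as Week 24 responders on an earlier or confounded window.

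How many are affected, and which arm gains, cannot be derived from the protocol. Under the assumed equal shares of 5% to 20%, with the planned 30% and 70%, even the widest recoding leaves a 32- to 38-point difference and power of at least 0.988 per comparison. The least favourable unequal split examined gives 27.5 points and 0.933. These figures depend on the 70% active rate. The issue is what the primary estimate means; sample size is not the obstacle to correcting it.

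**What to change.** Amend 9.5.2 and 9.5.5 before the Week 24 unblinding:

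1. Count as non-responders women coded Subject's Request whose specified reason is perceived lack of efficacy. Section 6.6.2.1 already requires that reason to be written on the exit form, so 6.6.2.1 and 9.5.2/9.5.5 can be made to agree without new data.
2. Count withdrawals for pregnancy as non-responders for the primary endpoint and, where the qualifying interval overlaps the pregnancy, for amenorrhea.
3. Count as non-responders women who used a prohibited bleeding-reducing drug affecting the assessment window: the hormonal agents in exclusion 16a to 16e, and the antifibrinolytics and mefenamic acid in 16g. Do not map all of 16g, because it also lists acetylsalicylic acid and anticoagulants, which do not reduce bleeding.
4. For the remaining withdrawals, keep the present rule and name an analysis with all missing Week 24 outcomes as non-response among the sensitivity analyses already promised in 9.5.5.

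Leave events already observed in the time-to-event endpoints as they are. The cost is wording, one derivation and a blinded review of exit-form reasons and concomitant medication. Response rates would fall slightly in all arms.

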9.6. STUDY SPECIFIC DATA ANALYSIS

An interim analysis was not planned for this study. However, a final analysis of Week 24 data, including the primary endpoint and BMD assessments will be performed once all randomized subjects have completed Week 24 or withdrawn from the study. The analysis will be performed by an unblinded team that will not be affiliated with the conduct, randomization and interpretation of theresults and reporting of this study.

During the Blinded Data Review meetings which will take place prior to each database lock, the Sponsor and clinical team members will only have access to aggregated summary tables using dummy treatment groups as well as blinded listings for discussion.

For this final analysis at Week 24, the baseline characteristics will be described using the Full Analysis Set. Subject disposition will be summarized but the summary will not provide specific information which could unblind individual subjects, for example the description of discontinuation. The primary endpoint and bone mineral density endpoint will be analyzed using the Full Analysis Set and the Per Protocol Set using data up to the Week 24 visit (included). Unblinded treatment groups will be presented in the corresponding tables without reporting the minimum and maximum values to help preserve the blind. Information of unblinded treatment will be removed from listings and listings will not be sorted by treatment group.

To respect the blind in the Week 24 analysis, the unblinded statistician will check that all tables do not contain information which allow identification of the treatment assignment of any subject. If it is the case, the table will be updated or removed from the analysis. Only after this has been checked and completed will the tables be provided to the Sponsor.

The Sponsor and study team will be fully unblinded after all subjects have completed the treatment period (Week 52) and the database has been locked.

A complete analysis will then be performed and the results will be summarized and described in an integrated Clinical Study Report.

The 24-week follow-up period will be reported in an addendum to the integrated Clinical Study Report.

Treatment allocation, individual P4 and E2 levels, Alkaline Hematin results (as of Study Day 1) will not be communicated and remain blinded up to the end of the study (Week 76 database lock) for the Investigator and the subject.

10. STUDY ADMINISTRATION

10.1. REGULATORY AND ETHICAL CONSIDERATIONS

This study is to be performed in accordance with the protocol, with the ethical principles that have their origin in the Declaration of Helsinki, the ICH Harmonized Tripartite Guideline for GCP (ICH E6(R1)), and all applicable local regulatory requirements.

10.1.1. Informed Consent

Before a subject can participate in the study, she must give written informed consent. The informed consent process will be in accordance with ICH GCP, and local regulatory requirements.

10.1.2. Regulatory Authority Approval

Before the study is initiated at a site, the Sponsor (or its delegate) will obtain approval to conduct the study from the appropriate regulatory authority in accordance with any applicable country-specific regulatory requirements.

10.1.3. Institutional Review Board Requirements

Before initiation of the study at a given site, written approval of the protocol, ICF and any information presented to potential subjects must be obtained from the appropriate Institutional Review (IRB). If any amendments to any of these documents occur during the study, notification or written approval as appropriate must be obtained prior to their implementation. The Investigator is responsible for ensuring that these actions occur.

Where required by local regulations, the Sponsor (or its delegate) is responsible for ensuring IRB approval of the study.

10.1.4. End of the study

For administrative and safety reporting purposes, the end of the study will be defined as the date of the final clinical database lock after the last subject has completed Week 76 visit. This provides a single and conservative definition across all study sites.

10.2. INVESTIGATOR RESPONSIBILITIES

The Investigator must be familiar with and conduct the study according to ICH GCP guidelines, the US Code of Federal Regulations and applicable local laws and regulations.

10.2.1. Coordinating Investigator

Where required by local regulations, national level coordinating Investigators may be appointed. Their responsibilities are outlined in a separate agreement with the Sponsor.

10.3. DATA MANAGEMENT

The Investigator or designee will be responsible for recording study data in the eCRF provided by the Sponsor. It is the Investigator's responsibility to ensure the accuracy of the data entered in the eCRFs. The data will be entered into a validated database. The Sponsor or delegate will be responsible for data processing, in accordance with the Sponsor (or delegate) data management procedures. Database lock will occur once quality assurance procedures have been completed. The database will not be locked before all data clarifications have been resolved and monitored and the decision on subject evaluation has been completed. PDF files of the eCRFs will be sent to the Investigator on completion of the study.

10.4. STUDY MONITORING

The Investigator must ensure that eCRFs are completed in a timely manner and must allow a Sponsor representative (e.g. CRA or study monitor) periodical access to subject records and all study-related materials. The frequency of monitoring visits will be determined by factors such as the design of the study, the frequency of subject visits and the site enrolment rate. In order to verify that the study is conducted in accordance with ICH GCP, regulatory requirements and the study protocol, and that the data are authentic, accurate and complete, the study monitor will review eCRFs and other study documents and will conduct source data verification.

Upon study completion, the Sponsor representative (e.g. CRA or study monitor) will visit the site to conduct a Study Termination Visit. This will involve collection of any outstanding documentation.

10.5. REVIEW COMMITTEE(S)

10.5.1. Data Monitoring Committee (DMC)

The DMC is a group of independent experts external to the study that, collectively, has experience in the management of subjects with uterine fibroids and in the conduct and oversight of randomized clinical trials.

Composition, responsibilities, rules for decision and procedures of the DMC will be described in more details in the DMC charter.

The DMC will be responsible for:

- safeguarding the interests of trial participants,
- assessing the safety of the IMP during the trial (reviewing unblinded safety data and AEs and SAEs, on a regular basis, as per charter prepared for the study).

The DMC will provide advisory support to the Study Director, the trial team and any other Sponsor representative. The Study Director will be responsible for promptly reviewing the DMC recommendations and determine whether expedited reporting of any safety issues, amendments to the protocol or changes in study conduct are required.

10.6. SUBJECT CONFIDENTIALITY

The Investigator and the CRA (or study monitor) representing the Sponsor must ensure that the subject's anonymity is maintained. In the eCRFs or other documents submitted to the Sponsor, the subject should not be identified by her name, but by her assigned SIN. If a subject's name is included on copies of documents to be submitted to the Sponsor, the name (except for initials) must be obliterated and the assigned SIN added to the documents.

The Investigator should keep a separate log of SINs, names, addresses, telephone numbers and hospital numbers (if applicable). Documents not for submission to the Sponsor, such as signed ICFs, should be maintained in strict confidentiality by the Investigator.

